### 9.3.2 Outcome definition and measures

During the observation period, which will span from the index date to the exit date for each offspring, outcome events will be identified based on ICD-10 codes recorded inpatient registries.

#### 9.3.2.1 Neurodevelopmental disorders, including ASD

The **index date** will be defined as the birth date of the offspring from which offspring will be observed for occurrence of the outcome of interest.

The **exit date/end of follow-up** will be defined as the end of the study period (31 December 2018 for Denmark and 31 December 2019 for Sweden and Norway), death, emigration (where available), reaching the age of 12 years for Denmark and Sweden and the age of 10 years for Norway or date of first diagnosis of the outcome at study, which-ever is the soonest.

The primary outcome is NDD including ASD, will be defined as a diagnosis of at least one the ICD-10 codes presented in codelist Table 10. Please note that ASD codelist is presented separately in the codelist Table 8, and NDD without ASD in the codelist Table 9.

#### 9.3.2.2 Congenital malformations

With the objective of investigating the risk of CM in offspring paternally exposed to valproate, all CM will be included in the comparative analysis, with the caveat that minor CM are usually under reported, therefore estimates could be under-estimated (17). However, a sensitivity analysis will be performed to address this concern (see section 9.7.5, *Broader definition of CM for secondary outcome*), for Norway and Denmark only.

The **index date (start of follow-up)** will be defined as the start of the 2nd trimester or 3rd trimester (12th or 22nd week of gestation), respectively for Norway and Denmark, and from offspring birth date for Sweden from which pregnancies will be followed up for the outcome of interest.

The **exit date/end of follow-up** will be defined as the end of the study period (31 December 2018 for Denmark and 31 December 2019 for Sweden and Norway), death, emigration (where available), reaching the age of 12 years for Denmark and the age of 10 years for Norway) or date of first diagnosis of the outcome at study, which-ever is the soonest.

The analysis of the secondary outcome of CM will be defined according to the presence of at least one of the following criteria:

- an ICD-10 code of CM among live births
- an ICD-10 code of CM in diagnosis/reason for spontaneous abortion/stillbirth (Norway and Denmark only)

The analysis will focus on all CMs, with further substratification by body system organ class. The ICD-10 codes for all CMs are presented in codelist Table 11.

---

 Period between LMP2 (date of conception) and date of birth is immortal - child must survive to be eligible and diagnosis of ASD cannot occur *in utero*

 CM will be classified according to the EUROCAT categories Guide 14 (section 3.3 in EUROCAT Subgroups of congenital anomalies (18)).

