In accordance with our proposal, the comparative evaluation of CM as a composite outcome will be secondary and therefore sample size estimation does not apply. For completeness an evaluation of the study power for a comparative evaluation based on major CM (since these comprise the smallest subgroup of CM but most serious) is presented below, with the assumption that this outcome is nested within the secondary composite outcome. Accordingly, the sample size should also be sufficient to observe the desired effect size for the comparative analysis of the composite secondary endpoint for Norway and Denmark.

The background incidence of major CM in pregnancies has been estimated to be 37.1 cases per 1000 pregnancies among live births (up to 1 year of age) or stillbirths (37). The combined incidence estimate of major CM associated with maternal valproate exposure (spina bifida, ventricular septal defect, atrial septal defect, cleft palate, hypospadias (boys only) and polydactyly) is 56.6 cases per 1000 pregnancies (17). It is acknowledged that this estimate does not contain all major CM and is therefore an estimate. According to the systematic review by Jentink et al. of 8 studies which explore the risk of major CM associated with valproate exposure in the first trimester compared to other AED, the effect size ranged from OR 2.9 (95% CI 1.1-7.7) for cleft palate to OR 5.5 (95% CI 1.4-25.4) for polydactyly; with the strongest association reported for hypospadias in boys (OR 6.6 (95% CI 2.8-16.6)), although the CI were wide reflecting the small numbers analysed. It would be reasonable to select the smallest effect size in the smallest subgroup of CM (i.e. major) to explore the power of this study to reject the null hypothesis of no difference. Assuming a minimum effect size of 2.5, where the background incidence was 3%, with 80% power, a study with a total sample size of 826 family linked offspring ( $n=413$ ) in the valproate monotherapy group and  $n=413$  in the comparator monotherapy group would be desirable.

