For exploratory objective 8, on the basis of lack of knowledge of the likely pattern of CM in offspring paternally exposed to valproate, it is of interest to describe the spectrum CMs according to the body system organ class affected from the malformation (see classification in section 9.3.2.2). Therefore, an exploratory objective is proposed to describe the spectrum of sub-types by organ class, with stratification as major or minor CM where feasible.

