### 9.7.5 Sensitivity analyses

The following sensitivity analysis will be conducted:

1. *Variation of exposure time window for primary outcome:* Examine the association between extended risk window of paternal valproate exposure (6 months) and NDD, including ASD, in the offspring to investigate if there is an effect of valproate exposure other than through the spermatogenic cycle.
2. *Outcome of interest restricted to ASD specifically (ignoring all other NDD diagnoses):* Investigate the risk of ASD in offspring paternally exposed to valproate (monotherapy), compared to lamotrigine or levetiracetam (composite monotherapy) treatment at the time of conception.
3. *Exclusion of offspring with a birth weight lower than 1000gr or born prior to 8th month of pregnancy, for primary outcome.* There are suggestions for evidence of association between preterm birth/low birth weight and NDD (47–49). If AEDs affect preterm birth and preterm birth affects NDD, this means that preterm birth could act as a mediator between AEDs and NDD. In the same way, if AEDs affect very low birth weight and very low birth weight affects NDD, this means that very low birth weight could act as a mediator between AEDs and NDD. Adjusting for a mediator introduces a bias, therefore this sensitivity analysis will be performed excluding extremely low birth weight, very preterm and extremely preterm newborns to explore the potential impact introduced by inclusion of this sub-population of offspring on the point estimate.
4. *Handling of missing diagnoses for CM outcome:* Since a lot of diagnoses/reasons for spontaneous abortions and stillbirth could be missing, due to under-reporting, a sensitivity analysis will be performed to investigate the risk of CM using a broader definition of the outcome. It will include all the ICD-10 codes of interest where available, as reported in section 9.3.2.2, for live births and spontaneous abortions/stillbirths as well as all spontaneous abortions/stillbirths without an ICD-10 code for the diagnosis/reason. The main advantage of this broader definition of the outcome would allow to include in the analysis under reported cases of CM, on the other hand missing diagnoses related to cases different from CM could be included.

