$$\sum_{i=1}^n \left( \frac{\sum_{j=1}^{k-1} \text{days} (\text{prescription}_{j+1} - \text{prescription}_j) * \text{WHO DDD}}{n. \text{pkg in prescription}_j * n. \text{dosage unit in each pkg}} \right) / n$$

where n is the number of patients and k is the number of prescriptions per patient.

Under the assumption of perfect compliance of each patient, if the Ratio for the overall population is between 0.8 and 1.2 then the WHO DDD is a good approximation of the reality; the more the ratio departs from the good approximation range the more the real daily dose prescribed diverge from the WHO defined daily dose. It is expected to have a good approximation to the reality for patients with the epilepsy indication for AEDs.

This measure will be affected both from the approximation of using the WHO DDD and the compliance of patients to the treatment. The less the compliance, the more the ratio departs from good approximation (0.8-1.2). Since the dose prescribed is not available, it will not be possible to assess what affected more the results.

Sensitivity analysis 8 will be performed only in the Primary Outcome Cohort for Descriptive Analyses

9. *Narrow case definition for secondary outcome - focus on CM in live births*: Since the population for analysis of the secondary outcome for Sweden is comprised of live births, the distribution of CM observed in this population is likely to reflect functional defects and minor morphological abnormalities, rather than major morphological abnormalities (usually associated with fatal outcome during gestation). A sensitivity analysis will therefore be performed on the corresponding live birth population for Norway and Denmark to describe the corresponding risk and underlying distribution of CM associated with live births.
10. *Continuous measure of cumulative exposure*: Investigate separately the risk of NDD, including ASD, as well as CM, in offspring paternally exposed to monotherapy treatment with valproate, lamotrigine or levetiracetam at the time of conception, using cumulative exposure to treatment. Cumulative exposure will be calculated as the total amount of DDD intake that a father is exposed to over the 3-months time window prior to LMP2 date, i.e. the sum of the DDD in all 14-day intervals as reported in Figure 8.

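### The sensitivity analysis cited for under-reported minor CM addresses a different problem, and the CM sample size is computed for major CM, for which no effect estimate is planned

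*Protocol*

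**What the plan says.** Section 9.3.2.2 makes all CM, major plus minor, the outcome of the CM comparison: "The analysis will focus on all CMs, with further substratification by body system organ class". It warns that "minor CM are usually under reported, therefore estimates could be under-estimated (17). However, a sensitivity analysis will be performed to address this concern", and names a section 9.7.5 analysis called "Broader definition of CM for secondary outcome". No item in 9.7.5 has that title.

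The item that does broaden the CM definition is item 4. Its stated reason is "Since a lot of diagnoses/reasons for spontaneous abortions and stillbirth could be missing, due to under-reporting", and what it adds to the case definition is "as well as all spontaneous abortions/stillbirths without an ICD-10 code for the diagnosis/reason". Item 9, "Narrow case definition for secondary outcome - focus on CM in live births", changes the population to live births. Items 5, 6 and 10 keep the all-CM outcome.

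Section 9.5 says that formal sizing does not apply to the secondary outcome but gives, for completeness, "an evaluation of the study power for a comparative evaluation based on major CM". The result is 826 offspring (413 per group) for a 3% background, an effect of 2.5 and 80% power. It then infers that the sample also suffices for the composite, because major CM is nested in it. Section 9.7.3.2.2 models the CM composite only. The one planned split by severity is the descriptive exploratory objective 8 in section 9.7.4, "with stratification as major or minor CM where feasible".

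**The concern.** Two gaps meet here. First, the protocol identifies a recording problem with minor CM and tells the reader that a named analysis deals with it. The analysis that exists deals with missing diagnoses in pregnancy losses. A reader of the report would take item 4 as evidence on minor-CM recording, which it cannot supply.

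Second, the endpoint with the numerical calculation is not one that will be estimated. Nesting ensures that every major CM is counted in the composite. It does not ensure that the composite has the same relative effect. If an effect were confined to major CM, the minor codes would pull the composite ratio towards 1, and no planned estimate would show it.

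The protocol treats the parallel case differently. ASD is also a nested endpoint used for sizing in section 9.5, and it receives its own comparison in sensitivity analysis 2. Major CM has its own code list (Table 12) but no comparison.

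Section 9.9.1 adds to the interpretive difficulty. It expects recorded CM in Norway (from week 12) to lean towards major abnormalities and in Denmark (from week 22) towards minor and functional ones. Section 9.7.6 pools the all-CM odds ratios of these two countries.

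**Working it through.** **Does any planned analysis address minor-CM recording?** Going through the CM items of section 9.7.5:

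- Item 4 changes the case status of non-live births without a coded reason. Live births and the Table 13 minor codes are untouched.
- Item 5 changes the comparator, item 6 the adjustment method, item 10 the exposure measure. The outcome stays all CM.
- Item 9 changes the population to live births. The codes stay all CM.

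None separates or removes minor CM.

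**Reproducing 826.** Inputs from section 9.5: background 3%, effect 2.5, power 80%, equal groups. The 5% level is stated there for NDD and ASD and is assumed to apply to CM. Two-sided testing is from section 9.7.3.1. Freedman's log-rank formula gives

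events = (1.96 + 0.84)² × ((1 + 2.5)/(1 − 2.5))² ≈ 42.7.

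With an exposed risk of 1 − 0.97^2.5 = 7.33%, the mean risk is 5.17% and N = 42.7/0.0517 ≈ 827. With 2.5 × 3% = 7.5%, N ≈ 814. The figure of 826 is reproduced within 3%, so the arithmetic is not at fault.

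**What nesting leaves open.** Suppose the effect is confined to major CM (3% against 7.5%) and minor-only CM adds m percentage points to both groups. The documents give no value for m, so 1 to 5 points is assumed. Then p₁ = 3% + m, p₂ = 7.5% + m, p̄ is their mean, and

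power = Φ{ [ (p₂ − p₁)√n − 1.96 √(2p̄(1 − p̄)) ] / √(p₁(1 − p₁) + p₂(1 − p₂)) }.

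Worked case m = 0, n = 413: (0.045 × 20.32 − 1.96 × 0.3154)/0.3138 = 0.944, so power is 83%.

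Worked case m = 5, n = 413: (0.045 × 20.32 − 1.96 × 0.4289)/0.4278 = 0.173, so power is 57%.

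| m (points) | Composite risk ratio | Power, 413 per group | n per group for 80% | Power, 790 per group |
|---|---|---|---|---|
| 0 | 2.50 | 83% | 385 | 98% |
| 1 | 2.13 | 76% | 454 | 96% |
| 2 | 1.90 | 70% | 521 | 93% |
| 3 | 1.75 | 65% | 586 | 90% |
| 4 | 1.64 | 61% | 650 | 87% |
| 5 | 1.56 | 57% | 712 | 84% |

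The 790 is the smaller of the two projections of valproate-exposed offspring in section 9.5 (about 860 in Norway, about 790 in Denmark), with a comparator group of similar size as assumed there. Adding the two countries (860 + 790 = 1,650 per group) gives about 99% or more at every m. These are crude two-group figures. They ignore weighting, clustering by father and between-country variance, all of which affect precision.

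**The case against.** The strongest reply is that little is lost. Section 9.5 offers the major-CM figure only for completeness and as a proxy; it does not promise a major-CM test. The comparative model matches the outcome as defined. Objective 8 may let readers see major CM by exposure group. The SAP, which is not at hand, could add a major-CM model. All of this stands. What is missing is a formal effect estimate, not every view of the data.

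Two stronger inferences are tempting and are not supported:

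- A reader might conclude from the 57% to 76% figures that the CM comparison is underpowered. They apply at 413 per group, the stated minimum. At the projected sizes power stays at 84% or more.
- A reader might conclude that poor recording of minor CM itself dilutes the composite. It works the other way: an unrecorded minor CM is not a case, so poorer recording means a smaller m and less dilution. If recording is similarly incomplete in both groups and false positives are few, absolute risks and precision fall but the ratio is largely preserved. The table models counted minor CM with no exposure effect, which is a separate question from under-reporting.

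Nor is it a hidden flaw that item 4 may count losses unrelated to CM as cases; the protocol says so itself.

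These points limit the consequence. They do not repair the statement in 9.3.2.2, which attributes to section 9.7.5 a check that is not there.

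**Conclusion.** The point holds. The stated check on minor-CM under-reporting is not delivered, and the endpoint that was sized has no planned effect estimate. The nesting argument shows that major CM are included in the composite, not that the composite carries a 2.5-fold effect. Under an effect confined to major CM and an assumed 1 to 5 points of unaffected minor-only CM, the composite ratio is 2.1 to 1.6.

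The cost in power is modest if the projections, taken here as the protocol gives them, are met. The main loss is interpretability: a composite odds ratio near 1, or one that differs between Norway and Denmark, could not be set against an estimate for major CM alone. This should be corrected, but it does not threaten the primary NDD analysis or invalidate the CM comparison.

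**What to change.** Add to section 9.7.5 a comparative sensitivity analysis with the outcome restricted to major CM (Table 12), using the same PS-weighted logistic model and the same Norway and Denmark pooling as the secondary outcome. Point section 9.3.2.2 to it, and state that it removes the under-recorded component rather than correcting for it. Cite item 4 only for missing diagnoses in spontaneous abortions and stillbirths.

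The cost is one more model per country and one pooled estimate, using a code list that already exists. The drawback is fewer events and a wider interval than for all CM.

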### 9.3.2.3 Case assessment

This will be undertaken to further assess offspring that will be identified as cases with the primary outcome of interest (NDD including ASD).

Due to data access restrictions it is not possible to undertake **manual** assessment of computerized profiles of NDD cases identified through diagnostic codes. Therefore, the assessment will be undertaken on all NDD including ASD cases (not a sample as originally intended), based only on available coded data for the live birth offspring.

The clinical code list for NDD including ASD refers to the following categories (please see Table 10):

- Intellectual disabilities
- Communication disorders
- Disorders of psychological development
- Hyperkinetic disorders
- Tic disorders
- Movement disorders

### Population

All offspring from the Primary Outcome Cohort for Descriptive Analyses who will be identified as having the outcome of interest (NDD including ASD).

Please note the original plan was to conduct a manual assessment, so only 20% of cases was going to be included. Since the updated plan simply uses recorded data and the assessment will be done programmatically, all cases will be included.

### Methods

Each offspring that will be identified as a case of NDD including ASD will be assessed, and categorized into one of the following categories:

**Probable case:** The offspring aged  $\leq 12$  years for Denmark and Sweden and aged  $\leq 10$  years for Norway will be considered a probable case if they satisfy the criteria that multiple diagnoses for NDD including ASD are recorded during follow-up, regardless of whether the same code is recorded multiple times or different codes are recorded

**Possible case:** The offspring aged  $\leq 12$  years for Denmark and Sweden and aged  $\leq 10$  years for Norway will be considered a possible case if they satisfy the criteria that only one diagnosis record for NDD including ASD is recorded during follow-up

Percentage of probably and possible cases across all exposure categories will be reported. The percentages of number of offspring identified as cases of NDD including ASD will be calculated over the total pregnancies in each group. The percentages of probable and possible cases will be calculated over the total number of offspring identified as cases of NDD including ASD in each group.

“Non-cases” will not be captured since the analysis focuses on offspring with at least one record indicating NDD including ASD.

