## **9.2.3 Overview of the family linkage**

### **9.2.3.1 Neurodevelopmental disorders, including autism**

[figure not shown]
For the purpose of the evaluation of NDD, including ASD, Figure 3 illustrates the registry linkage of the study participants, the paternal exposure period (3-months prior to LMP2 date, for further details please see footnote 10), follow-up period for the offspring (from birth to maximum 12 years of age for Denmark and Sweden and 10 years of age for Norway), and the look back periods for confounders for each linked family member (mother: 12 months prior to delivery, father: 12 months prior to LMP2 date).

---

 Non-live births are not included because a diagnosis of NDD cannot be made

 A patient is considered continuously enrolled in a specific time period if that patient had a contact with healthcare services (such as drug prescription or hospitalisation) prior to that period and if emigration or death were not notified after this contact.

[figure not shown]
 A patient is considered continuously enrolled in a specific time period if that patient had a contact with healthcare services (such as drug prescription or hospitalisation) prior to that period and if emigration or death were not notified after this contact.

[figure not shown]

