## 9.7.2 Descriptive Analyses

### 9.7.2.1 Cohort characteristics

Demographic characteristics of mother, father and offspring will be presented for both *the primary and secondary outcome cohort* and separately for *paternal exposure groups* (valproate and lamotrigine/levetiracetam (composite and separately) in monotherapy). Other characteristics (e.g. age at first diagnosis of outcome) and other co-existing risk factors for primary and secondary outcomes of interest (e.g. medication use within 3 months prior to LMP2 (paternal and maternal) and during pregnancy (maternal)), and concurrent relevant morbidities according to each relevant index date, will also be summarised. Thus, contingency tables reporting the characteristics of offspring with NDD, including ASD, as well as outcomes of CM occurrence by paternal and maternal exposure groups, will be provided. Summary description of the frequency of extremely low birth weight, very preterm and extremely preterm newborns will be provided for the primary outcome cohort, by paternal and maternal exposure group (a sensitivity analysis will be performed excluding preterm and low birth weight offspring, section 9.7.5). Summary description of the frequency of children exposed to AEDs

and/or diagnosed with epilepsy after birth will be provided (a sensitivity analysis will be performed including those children, section 9.7.5). Summary description of the frequency of stillbirth, spontaneous abortion, intrauterine growth retardation and perinatal mortality, associated to a diagnosis of CM, will be also provided. Data will also be stratified by age and calendar period. A descriptive table of the frequency of fathers who switch to or switch from an AED other than valproate, lamotrigine or levetiracetam, even if on monotherapy, will be provided. A descriptive table with a summary of the case assessments (see section 9.3.2.3), undertaken by study clinical investigators using the registry data on a random sample of cases, will be provided at aggregate level.

A STROBE (STrengthening the Reporting of OBservational studies in Epidemiology) diagram will be provided to show exclusions to be applied in order to create cohorts for analysis.

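### Case assessment counts repeat NDD diagnoses only during follow-up, but follow-up ends at the first NDD diagnosis, so a diagnosis confirmed at a later visit can never make a case probable

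*Protocol*

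**What the plan says.** Four parts of the protocol bear on this.

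- **Section 9.3.2** sets the window for finding outcomes: "During the observation period, which will span from the index date to the exit date for each offspring, outcome events will be identified".
- **Section 9.3.2.1** defines the exit date, which it equates with the end of follow-up. It is the earliest of end of study period, death, emigration, age 12 (10 in Norway), "or date of first diagnosis of the outcome at study, which-ever is the soonest".
- **Section 9.3.2.3, Methods**, grades every child already identified as an NDD case. Probable requires that "multiple diagnoses for NDD including ASD are recorded during follow-up, regardless of whether the same code is recorded multiple times", or that different codes appear. Possible requires that "only one diagnosis record for NDD including ASD is recorded during follow-up". Both grades carry the age limit of 12 (10 in Norway). The section defines no follow-up window of its own.
- **Section 9.7.2.1** promises a summary table of case assessments "undertaken by study clinical investigators using the registry data on a random sample of cases". Section 9.3.2.3 says that manual assessment is not possible and that all cases will be assessed from coded data by program.

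The ENCePP checklist in Annex 2 cites section 9.3.2.3 as the answer to item 7.3 (information bias) and item 10.6 (control of outcome misclassification).

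**The concern.** The grading asks whether a child's NDD diagnosis was recorded once or more than once. That is useful only if records after the first diagnosis can be seen, and the definition of follow-up excludes them.

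The grading matters because the primary outcome is broad. One code suffices, and Table 10 runs from intellectual disability to tremor, torticollis and unspecified mental disorder. Section 9.9.2 concedes that NDD is hard to diagnose, and the validation study it cites covers childhood ASD only. With manual review dropped, the probable/possible split is the only place where the study looks at whether an individual child's diagnosis recurs. If the split reflects same-day coding, readers of the report could wrongly take children re-diagnosed at later contacts for unconfirmed cases.

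There is also a risk of uneven application. Section 9.6.2 says that database processes differ by country, and section 9.7.1 presents case assessment by country. Two analysts could follow the text in two ways and produce percentages that cannot be compared.

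**Working it through.** No figure is involved, so the check sets the two rules side by side.

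**Inputs**

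1. Records count from index date (birth) to exit date (sections 9.3.2 and 9.3.2.1).
2. The exit date is the earliest of the listed events, including first NDD diagnosis (section 9.3.2.1).
3. Probable means two or more NDD records during follow-up, and possible means exactly one (section 9.3.2.3).

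**Reasoning**

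Let T1 be the date of a child's first NDD diagnosis.

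- The children graded are those already identified as cases, and outcomes are identified only up to the exit date. For each of them T1 therefore falls within follow-up, and the exit date is T1.
- No NDD record in the observation period precedes T1, because T1 is the first.
- Any NDD record after T1 is after the exit date and so outside follow-up.
- Hence the number of records during follow-up equals the number of records dated T1.

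**What the grades then mean**

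- Child A has one NDD record at T1 and further NDD records at later visits T2, T3 and T4. One record falls in follow-up, so the grade is possible.
- Child B has two NDD codes entered at T1 and no NDD record afterwards. Two records fall in follow-up, so the grade is probable.

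The child with repeated confirmation gets the weaker grade. The child with one contact and two codes gets the stronger one, because section 9.3.2.3 accepts different codes and does not ask for separate dates.

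**Does another passage change this?**

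- Section 9.2.3.1 describes follow-up as running from birth to at most age 12 (10 in Norway). That is an upper limit and does not remove the exit at first diagnosis.
- Annex 3B defines the NDD endpoint as the first recorded event within follow-up, which agrees with section 9.3.2.1.
- Section 9.3.2.3 is silent on the window.

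The size of the effect depends on the share of cases with several NDD records dated T1. The protocol does not give it. Table 5 notes that the Danish patient register holds primary and secondary diagnoses, so same-date multiples can occur.

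**The case against.** The strongest reply is that the intended meaning is plain. Each grade has its own age limit, which would be odd if counting stopped at first diagnosis, and accepting repeats of the same code suggests records gathered over time. Section 9.2.3.1 shows that the protocol sometimes uses follow-up loosely, and a programming rule may sit in the SAP. This stands as evidence of what the authors probably meant. It does not remove the conflict: the protocol itself fixes both rules, and they do not fit together.

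Three stronger readings are tempting, and the protocol does not support them.

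- *Nearly every case would be graded possible.* This needs the share of cases with same-date multiples, for which no figure is given. What is certain is only that no later-dated record can count.
- *This is the only check on outcome validity.* Sensitivity analysis 2 (ASD only) and sensitivity analysis 11 (narrow NDD code list) also test the outcome definition, and section 9.9.2 cites an external validation in which 94% of childhood ASD diagnoses in a Danish register met ICD-10 criteria. Case assessment is the only within-study check at the level of the individual case, which is a narrower claim.
- *The primary result is affected.* It is not. The primary outcome is the first recorded event, and the grading yields descriptive percentages that enter no model, exclusion or meta-analysis.

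The random-sample sentence in section 9.7.2.1 is a separate leftover. Section 9.3.2.3 explains that the sample was replaced, so a reader can resolve it. It adds nothing to the main point, but it is current text and should be corrected.

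**Conclusion.** The point holds as an internal contradiction that makes the stated grading rule give the wrong answer. Under the protocol's only formal definition of follow-up, a diagnosis confirmed after the first diagnosis date cannot make a case probable, and the split measures same-day multiple coding.

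The consequence is confined to the reported percentages of probable and possible cases by exposure group and country, and to the reliance that checklist items 7.3 and 10.6 place on them. The number of misgraded cases cannot be derived from the protocol, and the primary hazard ratio does not change. The conclusion rests on reading follow-up in section 9.3.2.3 as section 9.3.2.1 defines it. If analysts in fact counted later records, the percentages may already be sound, and only the text needs correction.

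**What to change.** In section 9.3.2.3, add that for case assessment only the window runs from birth to the earliest of age 12 (10 in Norway), death, emigration or end of study, and does not close at first diagnosis. State that multiple means NDD records on at least two separate dates, or report same-date multiples in a row of their own.

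In section 9.7.2.1, replace the investigator assessment of a random sample with programmatic assessment of all cases.

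The cost is a few sentences and a re-run of one descriptive table in each country, assuming the extracts keep records dated after the first diagnosis. One limitation remains: children first diagnosed late, or close to the end of the study, have less time for a second record. Section 9.7.5 notes that the three drugs were licensed in different periods, so this time may differ between exposure groups and should be noted wherever the percentages are compared. Restricting the table to cases with a minimum time after first diagnosis, or a Cox model on probable cases only, would be optional extras. The correction does not depend on them.
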